### 13.2.2 The Short Form 36 Score (SF-36)

The SF-36 will be scored using SF-36 Health Survey Manual for physical health and mental health dimensions, and all eight scales.

## 13.3 Appendix 3 - Compliance Classification

### 13.3.1 EA Compliance Measurement

The Imperial College Healthcare guidelines suggest that people with intermittent claudication should aim to exercise at least 3 times a week for a minimum of 30 minutes (90 min/wk). We measure a patient as being compliant if they have done 75% or more of this recommended amount by the end of the 12 weeks (810 minutes).

**Table A5 Exercise Advice Compliance Measurement**

Centre	Weeks	Instructions	Min of exercise per week 	Total min	75% of min
Imperial College Healthcare	12	3 times a week	90	1080	810
University Hospital Southampton	12	3 - 5 times a week	90 - 150	1080 - 1800	810
Royal Bournemouth & Christchurch Hospital	12	5 times a week	150	1800	1350
Taunton & Somerset	12	3 times a week	90	1080	810
Cambridge University Hospital	12	5 times a week	150	1800	1350
Dorset County Hospital	12	3 times a week	90	1080	810
Hull and East Yorkshire Hospitals 	12				
Newcastle Upon Tyne Hospital	12	3 times a week	90	1080	810
North Bristol	12	3 times a week	90	1080	810
Nottingham University Hospital	12	7 times a week	210	2520	1890

Patients are advised on the type of exercise but with no specification as to duration and frequency of exercise.

The minimum of exercise per week was estimated assuming the advice patients were given to exercise at least 30 minutes per session.

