## 4. PARTICIPANT ENTRY

### 4.1 Study setting and population

This study is open to all patients at the participating NHS sites with a diagnosis of IC meeting specific inclusion and exclusion criteria.

The sites have been selected with their respect to their ability or not to provide SET.

The following six able to provide a SET programme^:

1. Imperial College Healthcare NHS Trust
2. North Bristol NHS Trust
3. Hull and East Yorkshire Hospitals NHS Foundation Trust
4. University Hospital Southampton NHS Foundation Trust
5. Dorset County Hospital NHS Foundation Trust
6. St George's University Hospitals NHS Foundation Trust\*

^Authorised SET centres will be permitted to recruit patients who do not wish to attend SET classes using a randomisation list that will allocate participants to Exercise Advice + NMES or Exercise Advice alone.

The following six are not able to provide a SET programme:

7. Cambridge University Hospitals NHS Foundation Trust
8. The Newcastle Upon Tyne Hospitals NHS Foundation Trust
9. Taunton and Somerset NHS Foundation Trust
10. Nottingham University Hospitals NHS Trust
11. The Royal Bournemouth & Christchurch Hospitals NHS Foundation Trust

\*a dual centre; a SET programme is only recommended in patients residing in the Wandsworth catchment area

Imperial Clinical Trials Unit	NESIC Clinical Study Protocol V6.0 24/03/2020	Form Number CR001A-T
-------------------------------	---	-------------------------

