## **5. General Considerations**

### **5.1 Study Design**

The NESIC trial is a pragmatic, multicentre two-arm randomised controlled study stratified by centre. There are 11 participating centres in England, distributed according to local therapy provision between SET and exercise advice only. Initially 5 SET centres and 6 exercise only centres recruited to the trial until all the SET sample of patients was recruited, subsequently 3 SET centres (Imperial, Bristol and Hull) also recruited patients for the exercise only group. Subject to any patient specific restrictions, all participants will receive the best medical therapy (BMT), which include exercise advice, and if the patient has cardiovascular risk factors, then they will aim to control this, e.g. smoking cessation, hypertensive medication and controlling diet.

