## 5.4 Study Population

This study is open to all patients at the participating NHS sites with a diagnosis of IC and who meet all inclusion and exclusion criteria. The 11 sites have been selected with respect to their ability to provide SET. The protocol includes a list of the recruiting centres and specifies whether the centre provides SET, or only provides exercise advice (EA).

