#### 6.2 Per protocol Population

In SET centres the per-protocol population includes all randomized patients who participated in some or all the centre prescribed SET classes as defined in the protocol.

Participants who in SET centres did not attend any centre specific SET class are excluded.

For all centres (offering SET or not), participants who withdraw from the study before the primary outcome measurement at 3 months is carried out or withdraw from the study and explicitly decide to not allow use of the primary outcome data already collected will be excluded from this analysis set.

The per-protocol analyses will be carried out for the primary and secondary endpoints.

Imperial Clinical Trials Unit	STATISTICAL ANALYSIS PLAN	NESIC
-------------------------------	---------------------------	-------

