#### Summary scores

- Physical components score (PCS)
- Mental component score (MCS)

Imperial Clinical Trials Unit	STATISTICAL ANALYSIS PLAN	NESIC
-------------------------------	---------------------------	-------

- **Compliance Classification**

We have classified a participant as “compliant” if they have done at least 75% of the recommended target minutes for Device use, at least 75% of the recommended EA minutes performing exercises and attend at least 50% of SET sessions by the end of the treatment period. Then compliance can be dichotomised, coding “Yes, complied” if the patient complied with the recommended threshold treatment and “No” if patient did not comply. This classification is obtained by combining the compliance classification of the three instruments used to collect compliance information from each intervention (Device, SET and EA). Procedures for these classifications are outlined in Appendix 3 section 13.3).

For each treatment group, a patient is considered compliant if they are compliant for all of their assigned treatments. Therefore, for each of the treatment groups compliance is defined as follows:

- EA: compliant if done 75% or more of recommended level of EA (75% of minutes performing exercises recommended by centre)
- EA + SET: compliant if done 75% or more of recommended level of EA and attended 50% or more SET sessions held by centre.
- EA + NMES: compliant if done 75% or more of recommended level of EA and done 75% or more of recommended level of NMES usage
- EA + SET + NMES: compliant if done 75% or more of recommended level of EA, attended 50% or more SET sessions held by centre and done 75% or more of recommended level of NMES usage

These variables, excluding compliance classification, will be summarized at follow up time periods by treatment group using the ITT analysis set. Compliance classification will be summarised at the end of the intervention period. Summaries of continuous variables will be presented as mean and standard deviations if normally distributed, and as mean and inter-quartile ranges for skewed data. Categorical variables will be presented as frequencies and percentages.

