**Table A1. Overview of the Program Information by Centre (target SET per centre)**

SET Centre	Number of sessions per week (target)	Program duration by months	Total number of sessions
*Imperial College Healthcare	1	6	24
North Bristol	2	3	24
Hull and East Yorkshire Hospitals	3	3	36
University Hospital Southampton	1	2	8
Dorset County Hospital	1	2	8
Royal Bournemouth & Christchurch Hospital	1	3	12

\*Imperial SET classes typically last 6 months so extra classes beyond 3 months will be entered under unscheduled visit

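### SAP 6.2 ties the per-protocol exclusion to the type of centre, so read literally it drops exercise-only patients recruited at SET centres who were never assigned SET

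*SAP*

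**What the plan says.** **Per-protocol set.** In SET centres, SAP 6.2 admits randomised patients who took part in at least some of the SET classes, and adds: "Participants who in SET centres did not attend any centre specific SET class are excluded". The per-protocol analyses cover the primary and secondary endpoints. Neither sentence refers to what the patient was assigned.

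**Who recruited whom.** SAP 5.1 states: "Initially 5 SET centres and 6 exercise only centres recruited to the trial until all the SET sample of patients was recruited". It then says that Imperial, Bristol and Hull, all SET centres, went on to recruit for the exercise-only group. Protocol 5.3 covers these patients: they do not wish to attend SET, the site counts as nonSET for them, and the InForm database holds a SET list and a nonSET list at these sites. SAP 5.9 still describes randomisation by type of centre only.

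**Bournemouth.** Protocol 4.1 places "The Royal Bournemouth & Christchurch Hospitals NHS Foundation Trust" under the heading "The following six are not able to provide a SET programme". SAP 5.4 refers the reader to that protocol list for which centres provide SET. Yet SAP Table A1, whose first column is for SET centres, has a row for "Royal Bournemouth & Christchurch Hospital" (12 sessions), and Table A6 gives it a threshold of 6.

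**EA thresholds.** SAP 7.2 requires 75% of the centre's recommended EA minutes in all four groups. In Tables A3 and A5 the Hull row has no figures, and footnote 1 explains: "Patients are advised on the type of exercise but with no specification as to duration and frequency of exercise". St George's has no row in either table.

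**Cross-reference.** SAP 8.8.1 takes the definition of a complier from section 8.9.6.4, which holds only empty table shells.

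**The concern.** After SAP 5.1 and protocol 5.3, a SET centre is no longer the same thing as a centre whose patients are all assigned SET. SAP 6.2 still treats them as the same. The exercise-only patients at Imperial, Bristol and Hull were offered that route because they did not want the classes, so by design they attend none. Taken at its word, SAP 6.2 removes all of them from a planned analysis of the primary endpoint although they followed their allocation.

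The Bournemouth rows in Tables A1 and A6 make the centre label less reliable still, because the SAP then contains two answers to which centres are SET centres. The trial is unblinded (SAP 5.6), so a choice left open in the SAP would be made with outcome data in view.

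**Working it through.** **Step 1: reproduce the SAP's thresholds.**
- EA (Table A5): 0.75 × 12 weeks × minutes per week. 90 gives 810, 150 gives 1350, 210 gives 1890. All nine filled rows agree.
- SET (Table A6): 0.5 × sessions per week × 4 × months. Imperial 0.5 × 1 × 4 × 6 = 12; Bristol 0.5 × 2 × 4 × 3 = 12; Hull 0.5 × 3 × 4 × 3 = 18; Southampton and Dorset 0.5 × 1 × 4 × 2 = 4; Bournemouth 0.5 × 1 × 4 × 3 = 6. All six agree.

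The arithmetic is sound. The question is which patients the rules apply to.

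**Step 2: reconcile the centre lists.**
- Protocol 4.1 SET list: Imperial, Bristol, Hull, Southampton, Dorset and St George's (dual) = 6.
- Protocol 4.1 non-SET list: Cambridge, Newcastle, Taunton, Nottingham and Bournemouth = 5 names under a heading that says six; the dual site St George's makes 6.
- SAP 5.1: 5 SET + 6 exercise-only = 11. This fits the protocol list if St George's counts as exercise-only (6 − 1 = 5 and 5 + 1 = 6). That placement of St George's is inferred from the counts; the SAP does not state it.
- Tables A1 and A6: Imperial, Bristol, Hull, Southampton, Dorset and Bournemouth = 6 SET centres, against 5 in SAP 5.1. The mismatch stands wherever St George's is placed.

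**Step 3: apply SAP 6.2 to each kind of patient** (all with the 3-month outcome measured and no withdrawal).

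| Patient | Assigned SET | By centre, as written | By randomisation list |
|---|---|---|---|
| SET list, attended at least one class | Yes | Kept | Kept |
| SET list, attended none | Yes | Excluded | Excluded |
| nonSET list at Imperial, Bristol or Hull | No | Excluded | Kept |
| Bournemouth, EA or EA+NMES | No | Kept under protocol 4.1; excluded only if Table A1 is taken to govern | Kept |
| Cambridge, Newcastle, Taunton, Nottingham | No | Kept | Kept |

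The third row is the error. Because randomisation is stratified by centre, the loss falls on both arms, so the main damage is lost patients and a mix shifted towards SET, rather than a direct imbalance between arms. There is also a side effect. The Tobit model of SAP 8.2 includes both centre and group (SET or non-SET). If every centre is left with one group only, group cannot be separated from the centre indicators. The treatment coefficient can still be estimated.

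**Step 4: the EA gap.** Hull and St George's are 2 of 11 centres (18%). SAP 5.2.3 gives the general advice as 30 minutes, 3 to 5 times a week, that is 90 to 150 minutes a week, so the threshold could be 810 or 1350 (1350 / 810 = 1.67-fold). A patient who does 80 min/wk logs 80 × 12 = 960 min, which is compliant at 810 and not at 1350. Hull recruited both SET and exercise-only patients, so all four groups can hold patients without a threshold. The composite is undefined only for those who meet their other assigned components. Hull's SET threshold (18 of 36 sessions) and the NMES threshold (1890 min) are defined.

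**The case against.** The best defence is that the intended reading can be recovered. SAP 5.4 defers to the protocol on centre type, SAP 6.2 refers to the protocol for the SET classes, and protocol 5.3 says that SET sites count as nonSET for patients who decline classes. A careful analyst would probably keep these patients. This shows what was meant, but SAP 6.2 does not say it: its exclusion sentence is unqualified, and SAP 5.9 does not carry over the second list. A rule that decides who is in an analysis set should not depend on the analyst correcting it.

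Three stronger readings are tempting, and the documents do not support them.
- A reader might infer that a Bournemouth EA control who does the full 1800 minutes becomes non-compliant on 0 of 6 sessions. SAP 7.2 scores each patient only on assigned treatments, and Bournemouth has its own EA threshold of 1350 min, so that control is compliant.
- A reader might infer that Bournemouth's patients will be dropped from the per-protocol set. That needs an appendix table to override the protocol list to which SAP 5.4 defers. The Bournemouth rows are a contradiction to clear up and are not shown to cause exclusions.
- A reader might expect the missing EA thresholds to undermine the causal analysis. The complier-average trigger in SAP 6.1 uses SET attendance, and protocol 8.3 names EA compliance without requiring a yes/no cut-off.

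It is also fair to say that SAP 13.3.1 quotes 810 minutes, which could be taken as a default. But it is derived from Imperial's guideline, SAP 7.2 ties the rule to the patient's own centre, and Table A5 uses 1350 and 1890 elsewhere. One sentence would settle it.

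**Conclusion.** The concern holds for SAP 6.2. As written, the rule excludes the exercise-only patients of three SET centres from the per-protocol analyses of the primary and secondary endpoints, although they were never assigned SET. This rests on the literal wording of SAP 6.2 and on these patients attending no class, which follows from how protocol 5.3 selects them. Their number is not in the documents. The planned exercise-only group is 96 of 192 (protocol 3.2), which is only a ceiling, because six other centres also recruited to it.

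The Bournemouth rows are a real inconsistency (six SET centres against five) that adds to the confusion over centre labels. The two missing EA thresholds and the wrong section reference are smaller: they affect the compliance tables and the complier analysis, which the SAP files under sensitivity analysis. The ITT primary analysis and the sample size are not affected. The SAP should be corrected, but the point does not threaten the trial's main result.

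**What to change.** Before database lock:

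1. **Main change.** In SAP 6.2 and 13.3.2, define SET status by the randomisation list (SET or nonSET) from which each patient was randomised. Apply the no-class exclusion, and the matching inclusion sentence, only to patients randomised to SET.
2. **Bournemouth.** Delete its row from Tables A1 and A6. If it did run SET, correct the counts in SAP 5.1 and say which of its patients were randomised as SET.
3. **EA thresholds.** For Hull, state a default, for example 90 min/wk and 810 min as in SAP 13.3.1 and the Southampton row. For St George's, obtain the centre's own advice and add a row; use the default only if that advice is unquantified.
4. **Cross-reference.** Point SAP 8.8.1 to sections 7.2 and 13.3.

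The cost is a few lines and table cells in the SAP, plus one query to St George's. No new patient data are needed: the SET and nonSET lists are linked to the InForm database, and exercise minutes are already recorded in the diaries.

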### 13.3.2 SET Compliance Measurement

For SET, we know how many sessions per week each centre recommends, how many weeks they run the SET for (see table below) as well as how many sessions are attended by each patient. We measure a patient as being compliant if they have done 50% or more of the amount recommended by the centre by the end of the period the centre runs the SET (see table below).

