## 5.5 Treatment

There will be no change to the local site standard of care for patients with IC attributed to participation in this trial. Those sites with SET will continue to provide this intervention as per their normal standard of care and locally agreed protocol. The treatment period will last for 3 months.

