## **4. Study End Points**

### **4.1 Primary Endpoint**

Absolute walking distance (AWD) measured by standardised treadmill testing at 3 months (the end of the intervention period).

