### 5.8.1 Summary of Visit Schedule

Visit	Screening	Baseline*	Treatment Phase 0 - 3 months	Follow-up (months) †		
	1	2		3	4	5
				3 months	6 months	12 months
Informed consent	x					
Pregnancy Test	x					
Ankle Brachial Pressure index (ABPI) / positive stress test	x			x	x	x
Edinburgh Claudication Questionnaire						
Medical History	x					
Drug history	x			x	x	x
Peripheral pulse examination	x			x	x	x
Other exclusion criteria	x					
Randomisation		x				
Demography		x				
Vital Signs		x				
Quality of life questionnaires: EQ-5D-5L /SF-36 /ICQ		x		x	x	x
Treadmill test (ICD/ AWD)		x		x	x	x
Duplex Ultrasonography		x 		x 		
Laser Doppler Flowmetry		x 		x 	x	x
NMES training		x				
SET booking		x				
Compliance Diary (SET/device/EA)		x		x		
Resources use diary		x	x	x		
Weekly text messages			x			
Data logger		x	x			
Device experience questionnaire				x		
Safety reporting			x	x	x	x

Baseline and screening visit occur on the same day if both the researcher and participant agree that informed consent has been adequately considered with time to ask questions

women of childbearing potential a required to take a urine pregnancy test

At rest and during device use in device arm

[figure not shown]
NMES treatment groups only

SET centres only

For first 3 months (treatment period) or for whole duration they are completing SET classes (whichever is longer)

[figure not shown]
 The follow up information may be collected remotely (i.e. over the telephone completely or in combination with postal questionnaires) in the event that the participant is unable to attend the appointment in the clinic or the site is unable to accommodate the onsite visit due to COVID-19.

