Continuous	Supervised Exercise Therapy (SET) measured weekly from baseline to 3 months (recorded in participant's personalised diary) 
 
• Total number of weeks of exercise
 
• Number of therapy sessions attended each week
 
• Total minutes of exercise at home each week
 
	Summary in a table by treatment group. -Mean (SD) -Median (IQR)
	Neuromuscular electrical stimulation measured daily from baseline to at 3 months (recorded in participant's personalised diary) 
 
• Number of minutes of the NMES device use for each day
 
• Intensity setting of the NMES device for each day's use
 
	Summary in a table by treatment group. -Mean (SD) -Median (IQR)
	Exercise Advice (EA) measured weekly from baseline to 3 months (recorded in participant's personalised diary) 
 
• Recorded number of weeks of exercise reported in diary
 
• Recorded total minutes of exercise at home per week
 
	Summary in a table by treatment group. -Mean (SD) -Median (IQR)
Categorical	Device experience questionnaire(6 questions on patient experience using the devices)	Table of summary statistics
	Compliance	Table of proportion of compliance by treatment.
Subgroup Analysis Summary		
Continuous	Estimate the treatment effect in the SET vs the non-SET groups, at 3 months  Subgroup analysis 1: SET vs non-SET groups (NMES+SET+EA & SET+EA vs NMES+EA & EA).  Proportion of patients whose absolute walking distance at 3 months improved by 60 metres or more from baseline  Proportions of patients whose absolute walking distance at 3 months improved by 100 metres or more from baseline	Tobit Regression for absolute walking distance at 3 months with AWD at baseline , Treatment, Centre and Group as covariates.  Chi-square test at 3 months  Chi-square test at 3 months
	Estimate the treatment effect of NMES in the SET and non-SET groups, at 3 months  Subgroup analysis 2: NMES in the SET (NMES+SET+EA vs SET+EA)  Subgroup analysis 3: NMES in the non-SET (NMES+EA vs EA)  For both subgroups we will calculate:	Tobit Regression for absolute walking distance at 3 months with AWD at baseline ,Treatment, Centre and Group as covariates.

Imperial Clinical Trials Unit	STATISTICAL ANALYSIS PLAN	NESIC
-------------------------------	---------------------------	-------

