**Table A6 Supervised Exercise Therapy Compliance Measurement**

Centre	Sessions per week	Months	total session	50%
*Imperial College Healthcare	1	6	24	12
North Bristol	2	3	24	12
Hull and East Yorkshire Hospitals	3	3	36	18
University Hospital Southampton	1	2	8	4
Dorset County Hospital	1	2	8	4
Royal Bournemouth & Christchurch Hospital	1	3	12	6

\*Imperial SET classes typically last 6 months so extra classes beyond 3 months are entered under unscheduled visit

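### At the one centre with a six-month SET programme, classes held after the 3-month AWD can decide who counts as a complier for that AWD, because the SAP gives two cut-offs for counting SET attendance

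*SAP*

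**What the plan says.** Two parts of the SAP fix when the count of SET classes stops, and they differ.

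- **Three months.** SAP 7.2 requires participants to "attend at least 50% of SET sessions by the end of the treatment period". Protocol 5.5 dates that period: "The treatment period will last for 3 months". SAP Table 2 uses the same window for its compliance summaries: "Supervised Exercise Therapy (SET) measured weekly from baseline to 3 months". SAP 7.2 also summarises the classification when the intervention ends, which SAP 4.1 places at the primary endpoint: "Absolute walking distance (AWD) measured by standardised treadmill testing at 3 months (the end of the intervention period".
- **End of the centre's programme.** SAP 13.3.2 counts "50% or more of the amount recommended by the centre by the end of the period the centre runs the SET". For one centre Table A6 reads "Imperial College Healthcare 1 6 24 12", that is, one session a week for 6 months, 24 sessions, threshold 12. Its footnote adds: "Imperial SET classes typically last 6 months so extra classes beyond 3 months are entered under unscheduled visit".

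Two other places lean towards the programme-length count. SAP 7.4 lets the SET measurement period run from 2 to 6 months according to local policy and refers to Appendix 3. The footnote to the visit schedule in SAP 5.8.1 keeps the SET diary going "For first 3 months (treatment period) or for whole duration they are completing SET classes (whichever is longer").

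The classification is needed for SAP 8.8.1, which repeats the primary and secondary analyses in compliers only. SAP 8.8.1 gives 8.9.6.4 as the source of the definition, but that section holds only table shells, with no threshold and no cut-off.

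**The concern.** A complier analysis of a 3-month outcome should use only behaviour up to 3 months. If compliance is counted to 6 months, a patient's status can be settled after the treadmill test, by attendance that may itself depend on how well the patient was walking. The complier group is then partly selected on the outcome.

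The overall classification in 7.2 requires compliance with every assigned component. Exercise advice and device use are both counted over 12 weeks (13.3.1 and 13.3.3), so SET is the only component whose count can run past the endpoint. A patient who fails on SET is a non-complier whatever the other two show.

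If the analyst instead stops at 3 months, as 7.2 says, but keeps the tabulated threshold of 12, this centre faces a far stricter rule than the others. The trial is unblinded (SAP 5.6). As written, the choice between the rules could be made after the data are seen.

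**Working it through.** **1. Reproduce Table A6.** Total = sessions per week × months × 4 weeks; threshold = total ÷ 2. Sessions available by 3 months = sessions per week × 4 × the smaller of the programme length and 3 months.

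| Centre in Table A6 | Per week | Months | Total | Threshold | Held by 3 months | Share needed by 3 months |
|---|---|---|---|---|---|---|
| Imperial | 1 | 6 | 24 | 12 | 12 | 100% |
| North Bristol | 2 | 3 | 24 | 12 | 24 | 50% |
| Hull | 3 | 3 | 36 | 18 | 36 | 50% |
| Southampton | 1 | 2 | 8 | 4 | 8 | 50% |
| Dorset | 1 | 2 | 8 | 4 | 8 | 50% |
| Bournemouth | 1 | 3 | 12 | 6 | 12 | 50% |

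All six totals and thresholds agree with the SAP. Five programmes end by month 3, so the choice of cut-off matters only at the first centre. With 13 calendar weeks in 3 months, that centre would need 12 ÷ 13 = 92%.

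**2. Count to the end of the programme (13.3.2 as written).** The threshold is 12 of 24, and classes 13 to 24 follow the 3-month AWD. A patient with k of the first 12 classes needs 12 − k of the next 12. Every k from 0 to 11 is therefore still open at month 3, and only a patient with full attendance is already classed as compliant. A patient who attended 11 of 12 and then stopped is a non-complier. A patient who attended none of the first 12 and all of the next 12 is a complier for an outcome measured before the first class attended.

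**3. Count to 3 months but keep the threshold of 12.** The documents give no attendance rate. Assume independent attendance with probability p per class, and take p = 0.7 and p = 0.9:

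| Rule | Formula | p = 0.7 | p = 0.9 |
|---|---|---|---|
| 12 of 12 | p^12 | 1.4% | 28.2% |
| at least 12 of 13 | 13·p^12·(1 − p) + p^13 | 6.4% | 62.1% |
| at least 6 of 12 | binomial tail | 96.1% | over 99% |
| at least 12 of 24 | binomial tail | 98.8% | over 99% |

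**4. How often status is open at month 3 under rule 2.** On the same assumption this is 1 minus the first row: 1 − 0.014 = 98.6% at p = 0.7 and 1 − 0.282 = 71.8% at p = 0.9. With 13 weeks it is 1 − 0.064 = 93.6% and 1 − 0.621 = 37.9%. The last two rows of the table show that, if attendance stays constant, 6 of 12 and 12 of 24 accept similar proportions. The two rules part when attendance changes after month 3, and the documents give nothing from which to size that.

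**The case against.** A reader might infer that the SAP demands full attendance at this centre, so that nearly all its patients would be non-compliers. The documents do not support that. The result needs the cut-off from 7.2 and the threshold from Table A6 together, and neither section says this alone. Section 7.2 sets its own denominator, half of the sessions the centre held, which with its own cut-off plausibly gives 6 of 12. Section 13.3.2 alone gives 12 of 24. Section 7.2 also sends the reader to Appendix 3 for the procedure, and 7.4 and the 5.8.1 footnote fit a deliberate programme-length count. Even under the mixed rule, 28% would comply at 90% attendance, and 62% if 13 classes were held. The probabilities rest on assumed attendance rates and on independence between classes.

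A reader might also infer that the CACE results are distorted. SAP 6.1 makes that analysis conditional on a difference in SET uptake between arms, and measures uptake as classes attended over the centre's target. That is a ratio with no stated cut-off, and nothing shows that the 50% threshold enters it.

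The reach is small. One of the six centres in Table A6 is affected. The per-protocol set (6.2) asks only for some SET attendance, and 8.8.1 is a sensitivity analysis that already conditions on post-randomisation behaviour at every centre. Patients are not told their treadmill score (Protocol 5.4). For 6- and 12-month outcomes, counting a six-month programme is reasonable.

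All of this stands as a limit on size. It does not remove the problem: patients know their own symptoms without the score, and the reading that the SAP favours is the one that uses attendance after the outcome.

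**Conclusion.** The two cut-offs conflict and need to be reconciled. The rule that looks operative, in 13.3.2 and Table A6, lets classes held after the 3-month AWD decide who is a complier for that AWD at the six-month centre. If 7.2 is read as meaning the centre's own programme length, the sections agree but this problem remains. The resulting bias cannot be sized from the documents, which give neither attendance patterns nor the number of SET patients at this centre.

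Applying the threshold of 12 at 3 months would require 92% to 100% attendance there, against 50% at the other five listed centres. That is a risk created by the mismatch, not a rule the SAP states.

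The consequences are confined to the complier sensitivity analysis and the compliance classification tables. The ITT Tobit primary analysis does not use the classification, and an effect on the CACE analysis is not established. The point should be settled before the complier analysis is run, but it does not threaten the main result.

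**What to change.** For analyses of 3-month outcomes, define SET compliance in 7.2, 13.3.2 and Table A6 as attendance at no fewer than 50% of the sessions scheduled at the centre within the first 3 months. In Table A6 the six-month centre's threshold becomes 6 of 12, and the other five (12, 18, 4, 4 and 6) stay as they are. Summarise later attendance descriptively, and say so in 7.4 so that its longer window is not read as part of the classification. Correct the cross-reference in 8.8.1 to point to this definition instead of 8.9.6.4.

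The cost is aligned wording and one number. No new data are needed, because classes beyond 3 months at this centre are already entered separately. The downside is small: the definition ignores later classes, which may matter for the 6- and 12-month outcomes. If a programme-length measure is wanted for those, it should be specified separately.
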